6.8.4.1.2 Analysis

The number of subjects being discharged at 6 hours, the number of subjects being discharged between 6 and 12 hours and the number of subjects being discontinued after 12 hours will be summarized descriptively using the SAF.

The number of subjects being discharged between 6 and 12 hours will be summarized hourly. For subjects not being discharged, reasons for not being discharged will be summarized in categories using the SAF.

Discharge data from the day of first study drug intake and the day of re-initiation will be listed using the SAF.

6.8.4.2 Other baseline characteristics

Other baseline characteristics collected during Screening include chest X-ray, contraceptive methods, physical examination, ophthalmological assessments, tuberculosis test, viral serology results and urinalysis. These are defined as collected on the eCRF and no derivation is required.

6.8.5 Medical history and current medical conditions

6.8.5.1 Variables - medical history and cardiovascular medical history / risk factors

6.8.5.1.1 Medical history (except SLE history, cardiovascular medical history and cardiovascular risk factors)

Medical history includes all diseases or diagnoses recorded on the Medical History (except SLE history, cardiovascular medical history and cardiovascular risk factors) eCRF page.

Reported terms are mapped to PTs using MedDRA at time of database closure.

The variables of interest are the PT and the primary SOC.

Current medical conditions are diseases and diagnoses that are ticked as ongoing at Screening and without an end date before or equal to the study treatment start date. In the event of a partial end date that overlaps with first dose (e.g., 'May 2019' and first dose occurred on '23 May 2019') or if an end date is missing, the medical condition is considered to be current if ongoing is ticked 'Yes'.

6.8.5.1.2 Cardiovascular medical history

Cardiovascular medical history is collected on the Cardiovascular Medical History eCRF page. The same definitions apply as defined for the medical history (except SLE history, cardiovascular medical history and cardiovascular risk factors).

6.8.5.1.3 Cardiovascular risk factors

Cardiovascular risk factors are collected on the Cardiovascular Risk Factors eCRF page. The same definitions apply as defined for the medical history (except SLE history, cardiovascular medical history and cardiovascular risk factors).

6.8.5.2 Analysis - medical history and cardiovascular medical history / risk factors

Medical history and cardiovascular medical history / risk factors will be summarized using the FAS.

Summaries will be presented by primary SOC and PT, sorted by descending frequency based on the total column. The MedDRA version used for reporting will be specified in the footnote of the applicable output.

Medical history data will be listed using the SCR.

6.8.6 Previous and concomitant therapies

6.8.6.1 Variables

Previous and concomitant therapies are collected on the Previous/Concomitant Medications eCRF page. Both non-SLE and SLE therapies are collected on this page. Previous and concomitant medications are categorized as follows:

- Previous non-SLE therapies.
- Study-concomitant non-SLE therapies.
- Study-concomitant non-SLE therapies at baseline.
- Previous SLE therapies.
- Study-concomitant (background) SLE therapies.
- Study-concomitant (background) SLE therapies at baseline.
- Previous cardiovascular therapies.
- Study-concomitant cardiovascular therapies.
- Study-concomitant cardiovascular therapies at baseline.

A previous therapy is any therapy for which the end date of therapy is prior to first study drug intake in TP1. A study-concomitant therapy is any therapy, that is either ongoing at the start of study treatment or is initiated between the start of the study treatment and the EOS visit. A study-concomitant therapy at baseline is any therapy, that either started on, or is ongoing at, the study treatment start date.

The reported names are coded using the WHO drug code dictionary and the ATC class according to the most current version at time of database closure. The variables of interest are the PT (standardized medication name) and the ATC code level 4.

The WHO drug version used for reporting is specified in the footnote of the applicable output.

6.8.6.1.1 Non-SLE therapies

A non-SLE therapy is any therapy collected on the Previous/Concomitant Medications eCRF page which is not a SLE therapy [see Section 6.8.6.1.2] and not a cardiovascular therapy [see Section 6.8.6.1.3].

6.8.6.1.2 SLE therapies

SLE therapies are identified based on the protocol-defined background SLE therapies [see protocol section 5.2.2, D-22.031] and a list based on WHODrug Global B3/C3-format is maintained in a separate document for their identification.

An SLE therapy is any therapy collected on the Previous/Concomitant Medications eCRF page which is included in the above-mentioned list and which is not a cardiovascular therapy [see Section 6.8.6.1.3]. All SLE therapies will also be classified into the categories mentioned in protocol section 5.2.2, using this list.

6.8.6.1.3 Cardiovascular therapies

A cardiovascular therapy is any therapy administered for cardiovascular conditions or risk factors, reported on the Previous/Concomitant Medications eCRF page as:

- Cardiovascular medical history.
- Cardiovascular risk factors.

6.8.6.1.4 Duration of medications/therapies

The duration of medication/therapy in years is defined as:

- Duration of medication/therapy (years) = therapy end date – therapy start date + 1 day / 365.25.

6.8.6.1.5 Data imputation

The purpose of imputing therapy dates is only to determine if a therapy is study-concomitant and/or study-concomitant at baseline.

Incomplete therapy end dates will be imputed with the latest date possible, e.g., if the day is missing, the last day of the respective month will be imputed, or if day and month are missing, the last day of the respective year will be imputed. End dates that are completely missing will not be imputed and the therapy is considered as ongoing.

If a therapy start date is completely missing, the earliest of study treatment start date or (imputed) therapy end date will be imputed.

Partial therapy start dates will be imputed as follows:

- Therapy start day missing: if the (imputed) therapy end date is on or after study treatment start date (or missing) and the partial therapy start date is in the same month and year as the study treatment start date, the study treatment start date is used. Otherwise, the first day of the month is used.
- Therapy start day and month missing: if the (imputed) therapy end date is on or after study treatment start date (or missing) and the partial therapy start date is in the same year as the study treatment start date, the study treatment start date is used. Otherwise, the first day of the year is used.

6.8.6.2 Analysis

Number (%) of subjects having taken at least one previous, study-concomitant or study-concomitant at baseline treatment will be summarized by ATC class and individual PT within each ATC class using the FAS, by treatment group and overall. For tables describing background SLE therapies, the category from protocol section 5.2.2 and identified in the file mentioned in Section 6.8.6.1.2 will be used instead of the ATC class.

In addition, a table summarizing changes in background SLE therapies during TP1 will be produced.

All previous and concomitant therapies will be listed using the SCR.

6.9 Study treatment exposure

6.9.1 Exposure to treatment

6.9.1.1 Variables

Duration of exposure (months) to study drug is defined as the time elapsing between the [date of first study drug intake and the date of last study drug intake + 1 (in days)] / 365.25 × 12, regardless of any treatment interruptions.

Duration of exposure is also derived by treatment period (TP1 and TP2).

Exposure to study drug is also derived in categories (≤ 3 months [91 days], > 3 months and ≤ 6 months [183 days], > 6 months and ≤ 9 months [274 days], > 9 months) for analyses of TP1 and TP2 combined and in monthly categories for analyses of TP1 and TP2 separately, using the variable 'Duration of exposure (months) to study drug'.

6.9.1.2 Analysis

The following summaries will be provided:

- Study treatment exposure during TP1 using the SAF.
- Study treatment exposure during TP1 by subgroup (sex, SLE age group, race) using the SAF.
- Study treatment exposure during TP2 using the SAF-TP2.
- Study treatment exposure during TP1 and TP2 using the SAF.

Exposure data will be listed using the SAF.

6.9.2 Compliance

6.9.2.1 Variables

Overall compliance (%) will be assessed through study treatment accountability using the following formula:

$$\text{Accountability based compliance} = \left[\frac{\text{(number of tablets dispensed - number of tablets returned)}}{\text{number of tablets that should have been taken during the period*}} \right] \times 100$$

*The period is defined as the number of days during which study treatment should be taken as per actual visit dates.

If a subject did not return a kit, compliance will be set to missing for the respective period (e.g., between two visits). For the derivation of the overall compliance, the respective period will not be considered.

If a kit is replaced (e.g., because initial kit was lost by the subject), the initial kit will be ignored for the derivation of compliance.

The overall compliance will be categorized as:

- < 80%
- ≥ 80%

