2 STUDY DESIGN AND FLOW

2.1 Study design

This is a Phase 2b, multicenter, randomized, double-blind, placebo-controlled, parallel group study to evaluate the efficacy, safety, and tolerability of cenerimod in subjects with moderate to severe SLE.

Approximately 325 adult subjects with SLE will be randomized in a 1:1:1:1:1 ratio to placebo, 0.5, 1, 2, or 4 mg once daily of cenerimod, in addition to background SLE therapy.

Once randomized, all subjects will enter a 6-month double-blind study treatment period defined as Treatment Period 1 (TP1).

Subjects randomized to, and still receiving, placebo, 0.5, 1, or 2 mg at Month 6 will continue their study treatment up to an additional maximum of 6 months in Treatment Period 2 (TP2), for a total maximum of 12 months.

Subjects randomized to the 4 mg arm will receive study treatment at this dose for a maximum of 6 months in TP1. Afterwards, subjects in this group, still receiving this dose

at Month 6, will be re-randomized in a 1:1 ratio to placebo or cenerimod 2 mg to enter TP2 and will continue for a total maximum of 12 months

Subjects who discontinue treatment in TP1 will continue study FU, performing study assessments, up to maximum duration of 12 months.

At EOT, subjects will enter a 6-month FU period (4-month before protocol Version 5).

Treatment allocation is stratified by dose of OCS at Randomization (two strata: < 7.5 mg/day or ≥ 7.5 mg/day prednisone or equivalent), and by disease activity at Screening (with two strata: mSLEDAI-2K < 10 or ≥ 10).

The study will be conducted at approximately 180 sites in 21 countries notably from the regions of Asia Pacific, Eastern Europe, Latin America, North America, and Western Europe.

No interim analysis is planned. There will be three study analyses: the Month-6 analysis, the Month-12 analysis and the final EOS analysis. Month-6 analysis will be performed when all randomized subjects have completed TP1 or discontinued the study. Month-12 analysis will be performed when all randomized subjects have completed TP2 or discontinued the study. Final EOS analysis will be performed when all randomized subjects have completed the post-treatment follow-up period or discontinued the study.

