FACIT-Fatigue, PGIS-F, PGIC-F, SF-36v2™, and Lupus QoL		X		
Chest X-ray ⁽⁵⁾		X		
Vital signs: SBP/DBP* ^{(6) (7)}		X	X	
12-lead ECG* ⁽⁷⁾		X	X	
ECG Holter* ⁽⁸⁾			X	X
Echocardiography ⁽⁴⁾		X		
Spirometry*		X		
Ophthalmological examinations		X		
OCT		X		
PK sampling* ⁽⁹⁾			X	

PERIODS	Name	UNSCHEDULED		
	Duration	NA		
VISITS	Number	U1, U2, ...	I1	I2
	Name	Unscheduled ⁽¹⁵⁾	Re-initiation	
	Time	Any day between Day 1 and EOS (assessments to be performed as applicable)	Re-initiating study drug after interruption lasting more than 7 days between Day 1 and Day 14	
Hematology and blood chemistry* ⁽¹⁰⁾		X		
Pregnancy test ⁽¹¹⁾		X		
Viral serology / TB test		X		
Urinalysis (dipstick)		X		
SLE biomarkers		X		
Urine protein-to-creatinine ratio		X		
Study treatment dispensing/return and accountability			X	
AEs ⁽¹²⁾ / SAEs ⁽¹²⁾		X	X	

One month is considered to be 30 days.

Day 1 (date of Randomization visit) is to be used as the reference date for the purpose of calculating the subsequent visit dates (and time windows).

For WOCBP, the serum pregnancy test at Visit 1 must be performed at least 3 weeks before the urine pregnancy test performed at Visit 2 prior to Randomization.

* Study treatment should not be taken before the assessment (i.e., SBP/DBP, ECGs, spirometry, laboratory tests, and PK sampling).

- (1) Prior to Randomization, the following central laboratory results must be available to confirm eligibility: ANA, anti-dsDNA, anti-HAV IgM, Hepatitis B surface antigen, Hepatitis C antibodies (anti-HCV IgG or IgM), anti-HEV IgM and/or IgG, HEV-RNA PCR (as needed), HIV1 and HIV2, varicella-zoster virus IgM antibody, urine protein-to-creatinine ratio, ALT/AST/TBIL and pregnancy test (if applicable).
- (2) A complete physical examination (i.e., inspection, percussion, palpation, and auscultation) will only be performed at Visits 1, 2, 3, 5, 8, 11, 14, and 15. For all other visits, a symptom-driven abbreviated physical examination will be performed in order to capture assessments needed for the SLEDAI-2K, the PGA, the BILAG, and the SFI.
- (3) Height only at Screening. Body weight should be measured as part of BILAG assessment at each applicable visit and recorded in the source documentation. If clinically relevant, body weight collected outside Screening, EOT and EOS visits may be reported as an Unscheduled assessment.

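### The replaced-kit rule for compliance drops the initial kit's tablets but not the days it covered, and its precedence over the non-returned-kit rule is undefined

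*SAP*

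**What the plan says.** SAP 6.9.2.1 defines accountability-based compliance as a percentage.

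- **Numerator:** "number of tablets dispensed - number of tablets returned".
- **Denominator:** "number of tablets that should have been taken during the period". A footnote to the formula adds: "The period is defined as the number of days during which study treatment should be taken as per actual visit dates".
- **Kit not returned:** "If a subject did not return a kit, compliance will be set to missing for the respective period (e.g., between two visits"). The next sentence leaves that period out of overall compliance.
- **Kit replaced**, with loss by the subject given as the example: "the initial kit will be ignored for the derivation of compliance". Nothing is said about the days before the replacement.
- **Cut-off:** "The overall compliance will be categorized as" below 80%, or 80% and above. No cut-off is given for a single between-visit interval.

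SAP 6.9.2.2 summarises compliance descriptively, overall and separately for TP1 and TP2, on the FAS and FAS-TP2, and lists it.

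**The concern.** Kits enter the formula only through the numerator. Ignoring the initial kit therefore removes the tablets taken from it. The denominator is fixed by visit dates, so the days on which those tablets were due remain, and a subject who took every dose appears to have missed all doses before the replacement.

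The neighbouring rule makes this harder to read. A lost kit is normally also a kit that was not returned. Under the non-returned rule the whole interval is dropped; under the replaced-kit rule only the kit is. The SAP does not say which applies, so two programmers could report a missing value and 33% for the same subject, both following the text.

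At stake are the correctness and reproducibility of the compliance table and its < 80% category.

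**Working it through.** The documents give no compliance figure to reproduce, so the formula is applied to a subject with perfect intake.

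**Inputs**

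- Dosing is "0.5, 1, 2, or 4 mg once daily of cenerimod" or placebo (SAP 2.1). One tablet per day is an assumption; the documents do not give tablets per dose.
- Visits with dispensing are monthly and "One month is considered to be 30 days" (SAP 12.1), so a period is P = 30 days, TP1 is 180 days and 12 months is 360 days.
- The kit is lost and replaced after d days, with no missed dose (assumption).
- Overall compliance is total tablets over total days. This is an assumption, because the SAP does not say how periods are combined. With equal periods the mean of the period values agrees: for one day-20 loss in TP1, (5 × 100 + 33.3)/6 = 88.9%, and 160/180 = 88.9%.

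**Step 1: the interval.** True compliance is 100%. As written, the score is (30 − d)/30, an understatement of d/30. Overall compliance after one such event is (180 − d)/180 or (360 − d)/360.

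| d | Interval | TP1 (180 days) | 12 months (360 days) |
|---|---|---|---|
| 0 | 100% | 100% | 100% |
| 6 | 80.0% | 96.7% | 98.3% |
| 10 | 66.7% | 94.4% | 97.2% |
| 20 | 33.3% | 88.9% | 94.4% |
| 29 | 3.3% | 83.9% | 91.9% |

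**Step 2: when overall compliance falls below 80%.** The days removed must exceed 0.2 × 180 = 36 over TP1, or 0.2 × 360 = 72 over 12 months.

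- One loss removes at most 29 days, so one loss with full TP1 follow-up leaves at least 151/180 = 83.9%.
- With F days of follow-up, one loss after d days crosses when (F − d)/F < 0.80, that is F < 5d. For d = 20 this means F < 100; at F = 90 the value is 70/90 = 77.8%.
- Two day-20 losses give 140/180 = 77.8% over TP1 but 320/360 = 88.9% over 12 months.
- Over 12 months two losses remove at most 58 days, below 72, so at least three late losses are needed.

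**Step 3: the alternatives.**

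- Removing the initial kit's days as well gives (30 − d)/(30 − d) = 100%.
- Setting the period to missing leaves the other periods, all at 100%.
- Counting the lost kit as fully used errs the other way: with a 30-tablet kit (assumed) and d = 10, (30 + 20)/30 = 167%. Leaving its tablets out is therefore sensible; the gap is in the denominator.

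**The case against.** The strongest reply is that the SAP is silent on the denominator. Ignoring a kit for the derivation could mean ignoring its days as well as its tablets, or the non-returned rule could already govern a lost kit, in which case no adherent subject is scored low.

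Part of this stands: the SAP does not expressly order the days to be kept. But its only definition of the due days runs by visit dates, and where it wants a period dropped, in the preceding rule, it says so. The natural reading keeps the days. Treating the replacement visit as the start of a new period does not help, because the first part still has due days and a numerator of zero unless it too is dropped. Because loss is the example given for replacement, the replaced-kit sentence looks like the specific rule for a lost kit, but precedence is not stated.

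A reader might also infer that one lost kit makes an adherent subject non-compliant. The documents do not support that. The 80% cut-off belongs to overall compliance, there is no shortfall at d = 0, and one loss over a full TP1 leaves at least 83.9%.

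Nor is bias between arms shown. The rule is the same in every blinded arm, and the primary MMRM (SAP 7.2.5) uses the FAS under a treatment-policy strategy without compliance as a term. The documents show no link from the 80% category to the Per-Protocol Set; the detailed exclusion reasons are kept in a separate document (SAP 4.1.4).

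**Conclusion.** The point holds as a minor defect in a descriptive derivation. As written, an adherent subject's compliance is understated by d/30 for an interval in which the kit is replaced after d days: a score of 33.3% at d = 20, no effect at d = 0. In overall compliance the effect is mostly diluted. It moves a fully adherent subject below 80% only with short follow-up or repeated losses, and the < 80% count would then be too high.

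This rests on one tablet per day, 30-day periods, immediate replacement and pooling across periods. The TP1 figure of 77.8% affects the category only for a subject whose treatment ends at about Month 6, or if the cut-off is also applied to TP1 alone, which the SAP does not state. The documents give no frequency of replaced kits, so the number of subjects affected cannot be estimated.

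**What to change.** Add one sentence to SAP 6.9.2.1, along these lines: *A period in which a kit was replaced is handled like a period with a non-returned kit (compliance missing, period excluded from overall compliance), unless the replacement took place before any dose was due from the initial kit; in that case only the replacement kit is counted.* This settles both the denominator and the precedence.

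The cost is the sentence, a matching programming specification and slightly less compliance information for those periods.

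Counting expected tablets only from the replacement date is a weaker alternative, because it hides doses missed between loss and replacement. For example, with 10 doses taken, 5 days without drug and then 15 doses, true compliance is 25/30 = 83.3%, but counting from the replacement gives 15/15 = 100%.

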6.9.2.2 Analysis

Overall study compliance will be summarized using descriptive statistics by treatment group using the FAS. The “Not re-randomized / Ex-4 mg” group will also be displayed.

Compliance will also be summarized by period using the FAS for TP1 and the FAS-TP2 for TP2 (also including cenerimod 0.5 mg, 1 mg, 2 mg and placebo groups).

Compliance will be listed using the FAS.

6.10 Pharmacokinetic variables

PK plasma concentrations are collected 6 h after study drug administration on Day 1 (initiation or re-initiation) and pre-dose at Visits 3 (Month 1), 4 (Month 2), 5 (Month 3), 8 (Month 6), 14 (Month 12 or premature EOT), and at EOS.

To prevent unblinding, the results of the PK data are not communicated to the investigator, study personnel, subjects, Clinical Research Associates, or any sponsor or vendor/CRO personnel involved in the conduct of the study.

Results will be transferred by the bioanalytical laboratory for PK measurements to the sponsor and CRO personnel involved in the conduct of the study only after database lock.

6.10.1 Variables

Plasma concentrations are provided by the biomarker laboratory. Thus, no derivations are required.

6.10.2 Analysis

For PK variables quantitative descriptive statistics (including geometric mean and 95% CI) for plasma concentrations will be presented on the day of first study drug intake, the day of re-initiation and over time (Month 1, 2, 3, 6, 12, premature EOT, EOS), by visit and treatment group using the PKS.

The plasma concentration-time profiles of the values over time will be provided in figures (boxplot per treatment group and visit, from baseline to EOS) using the PKS.

A listing of PK data will be produced using the PKS.

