2.3.2 Treatment periods

The study comprises 2 treatment periods: TP1 and TP2.

TP1 lasts for 6 months. It starts with the administration of the first dose of study treatment, after subject randomization, and ends at the Month 6 visit.

Starting at the Month 6 visit, TP2 lasts for up to 6 months and ends at the Month 12 visit.

If a randomized subject discontinues treatment prematurely in TP1 or TP2, the subject will have a premature EOT visit, stay in the study, and complete all protocol-mandated visits up to the Month 12 visit (unless the subject withdraws consent earlier).

At the time of the Month 12 visit, the EOT visit will take place.

Furthermore, at this time the EOS visit will take place for subjects with premature EOT occurring at least 6 months prior to the Month 12 visit. For subjects with premature EOT occurring less than 6 months prior to the Month 12 visit, the 6-month FU period must be completed in its entirety. For example, if a subject has premature EOT at Month 8 occurring four months prior to the Month 12 visit, Month 9, Month 10, Month 11 and Month 12 visits, also functioning as FU1, FU2, FU3, and FU3a, are conducted as planned, along with FU3b and EOS visits after the Month 12 visit. This completes 6 months of follow-up.

[figure not shown]

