2.3.3 Follow-up period

This period starts after the EOT visit and lasts 6 months until the EOS visit.

For the first 5 months after the EOT visit, subjects will have to conduct monthly FU visits or phone calls at FU1, FU2, FU3, FU3a, and FU3b, to collect information on AEs/SAEs and/or pregnancy. For subjects that discontinue treatment prematurely, some or all FU visits may be replaced by scheduled visits.

EOS should occur 6 months after the EOT but can occur later for subjects that prematurely discontinue treatment before Month 8. Study periods are displayed in [Figure 1](#).

Figure 1 Study design ID-064A202 (CARE)

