- (4) Echocardiography will be performed at Visit 1 (Screening) preferably within 30 days prior to Randomization for all subjects and at Visit 8 (Month 6) in approximately 175 subjects, as part of the ancillary study. In the event of premature study treatment discontinuation during TP1 (i.e., before Visit 8), echocardiography will be performed at pEOT visit and will not be required at Visit 8.
- (5) A chest X-ray that has been performed within 6 months prior to Screening can be used (in this case, there is no need to repeat the chest X-ray at Screening).
- (6) At each pre-dose assessment, SBP/DBP measurements will be performed twice in the supine position.
- (7) On Day 1 and at Re-initiation visit, SBP/DBP assessment and 12-lead ECG will be done pre-dose and hourly until 6 h post-dose; after 6 h, subjects may be discharged if they meet the discharge criteria, otherwise SBP/DBP assessments and 12-lead ECG will be performed hourly until discharge criteria are met. If discharge criteria are not met after 12 h, the subject must be permanently discontinued. At all other visits, only pre-dose SBP/DBP assessments and 12-lead ECG will be performed.

- (8) On Day 1 and at Re-initiation visit, 24-hour ECG Holter should start before dosing. The subject must return to the site on Day 2 (Visit 2a) / Re-initiation (Visit I2) for removal of the device after 24-hour recording.
- (9) On Day 1 and at Re-initiation visit, PK samples will be collected 6 hours after dosing. At Visits 3, 4, 5, and 8, PK samples will be collected pre-dose. At pEOT visit, in the event of premature treatment discontinuation during TP1 (i.e., before Visit 8) and at EOS visit, PK samples will be collected at any time during the visit and will not be required at Visit 8.
- (10) Hematology assessments, including coagulation tests will be performed at each visit until EOS, except FU2, FU3 and FU3a, and FU3b visits.
- (11) Serum pregnancy tests will be performed at Screening and EOS. Urine pregnancy tests will be performed at all other visits. To ensure compliance, the study personnel must remind WOCBP at each visit to use the methods of contraception defined for this study from the Screening visit until 6 months after taking the last dose of study treatment.
- (12) All AEs and SAEs occurring after signing the ICF and up to 6 months after study treatment discontinuation must be reported.

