- (13) Sample for SLE biomarkers analyses will include: SLE biomarkers serum sample, serum EDTA sample and PAXgene sample.
- (14) If the subject discontinues study treatment prematurely, the pEOT visit should preferably take place no later than 7 days after last study drug intake. Subjects who prematurely discontinue treatment will remain in the study and continue to perform all assessments as per planned visit schedule. See Section 5.1.7 for additional details on premature discontinuation of study treatment.
- (15) Unscheduled visits may be performed at any time during the course of the study. Recording the changes in concomitant medications and in background SLE therapies since the last visit needs to be performed at each unscheduled visit. Further assessment including body weight, chest X-ray, 12-lead ECG, SBP/DBP, echocardiography, SLEDAI-2K, PGA, BILAG, FACIT-Fatigue Scale, PGIS-F, PGIC-F, SF-36v2™, Lupus QoL, laboratory assessments and other disease activity assessments may be performed at the discretion of the investigator.
- (16) Applicable for subjects having completed TP2 according to the protocol schedule up to Month 12 / EOT (Visit 14).

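### SAP 6.10.2 summarises plasma concentrations by visit label, so the EOS, premature EOT and early trough columns pool samples taken at very different times since the last cenerimod dose

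*SAP*

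**What the plan says.** **Summary.** SAP 6.10.2 gives descriptive statistics, including the geometric mean and 95% CI, "over time (Month 1, 2, 3, 6, 12, premature EOT, EOS), by visit and treatment group using the PKS". Boxplots are also per treatment group and visit.

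**Sampling.** SAP 6.10 places the later samples "pre-dose at Visits 3 (Month 1), 4 (Month 2), 5 (Month 3), 8 (Month 6), 14 (Month 12 or premature EOT), and at EOS". In SAP 12.1, footnote 9 says of the premature EOT (TP1) and EOS visits that "PK samples will be collected at any time during the visit and will not be required at Visit 8".

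**When EOS happens.** SAP 2.1: "At EOT, subjects will enter a 6-month FU period (4-month before protocol Version 5". SAP 2.3.2 sets EOS at Month 12 for early stoppers: "at this time the EOS visit will take place for subjects with premature EOT occurring at least 6 months prior to the Month 12 visit". SAP 2.3.3 adds: "EOS should occur 6 months after the EOT but can occur later for subjects that prematurely discontinue treatment before Month 8". The schedule's EOS timing of 6 months ±7 days after the last dose is footnoted (16) to subjects who completed TP2 on schedule.

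**When premature EOT happens.** Footnote 7 requires permanent discontinuation if discharge criteria are not met after 12 hours, so Day 1 is possible. Footnote 14 only prefers the visit within 7 days of the last intake, and says early stoppers "continue to perform all assessments as per planned visit schedule".

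**Rules that might sort the samples.** The PK Analysis Set (4.1.8) has no criterion on time since last dose. It says reasons for excluding a sample will be documented before unblinding, but lists no criteria. The Table 4 windows (5.4.4) are for efficacy and safety, end at Day 375 and have no EOS or premature EOT row.

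**Half-life.** COVID-19 addendum section 2.3 gives 12–22 days. The SAP revision history for version 5.0 cites evidence of a longer half-life, without a figure.

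**The concern.** For a drug that takes weeks to accumulate and weeks to clear, a concentration can be interpreted only with the dosing time behind it. A visit label supplies that for a subject on treatment at a fixed visit. It does not do so for EOS or premature EOT, or for a Month 1, 2 or 3 sample from someone who has already stopped.

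At stake is what the tables can tell a reader. For subjects who complete TP2, EOS is the only scheduled PK sample in the post-treatment follow-up, so it is where a reader will look for evidence of washout. A geometric mean over an unknown mix of elimination times does not show how much drug remains at any stated time.

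**Working it through.** **1. The plan's own example.** The rule in SAP 2.3.2 is: EOS month = max(12, EOT month + F), with F = 6 under Version 5 and F = 4 before. The SAP's example has EOT at Month 8: max(12, 8 + 6) = 14, and 14 − 8 = 6 months, as stated.

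**2. Interval from EOT to EOS under that rule.**

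| EOT | F = 6 | F = 4 |
|---|---|---|
| Day 1 | 359 days | 359 days |
| Month 1 | 11 months | 11 months |
| Month 3 | 9 months | 9 months |
| Month 5 | 7 months | 7 months |
| Month 6 | 6 months | 6 months |
| Month 8 | 6 months | 4 months |
| Month 12 | 6 months | 4 months |

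The Day 1 row uses Month 12 = Day 360 (Table 4): 360 − 1 = 359 days, and 359 / 30.44 = 11.8 months. The range is therefore about 4 to nearly 12 months. (With F = 6 the interval exceeds 6 months only for EOT before Month 6. The Month 8 limit in 2.3.3 fits F = 4, so 2.3.2 and 2.3.3 need to be reconciled.)

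**3. What the interval does to the concentration.** Assume first-order decay, 2^(−t/h), from the same starting level. The ratio of two samples d days apart is 2^(d/h). The 350-day case is a stop on about Day 10 with EOS at Day 360.

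| Half-life h (days) | 120 vs 180 days, 2^(60/h) | 180 vs 350 days, 2^(170/h) |
|---|---|---|
| 12 (addendum) | 32 | about 18,400 |
| 22 (addendum) | 6.6 | 212 |
| 30 (assumed) | 4.0 | 51 |
| 40 (assumed) | 2.8 | 19 |

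An early stopper also starts from a lower level, so the second ratio is, if anything, too small.

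**4. What the pooled EOS mean represents.** If a share w of a group is sampled at 120 days and the rest at 180, the geometric mean equals the concentration at day 120w + 180(1 − w). That is day 165 for w = 0.25 and day 150 for w = 0.5. The documents do not give w, so the time the mean stands for is unknown.

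**5. Premature EOT.** With daily dosing, the share of steady state reached by day t is 1 − 2^(−t/h). The loss over a 7-day lag to the visit is 1 − 2^(−7/h).

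| h (days) | Day 14 | Day 90 | Lost in a 7-day lag |
|---|---|---|---|
| 12 | 55% | 99% | 33% |
| 22 | 36% | 94% | 20% |
| 30 | 28% | 88% | 15% |
| 40 | 22% | 79% | 11% |

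One column holds all of these.

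**6. Months 1 to 3.** Footnote 14 keeps early stoppers on the visit schedule, and footnote 9 waives PK only at Visit 8. A subject who stops on Day 10 can contribute samples on Days 30, 60 and 90, when 20, 50 and 80 days off drug. The documents give no share of such subjects, so no size is attached.

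**7. Placebo / Ex-4 mg.** SAP 5.1 defines overall EOT as the later of the two period end dates, which here is a placebo intake. For a completer the last cenerimod intake is near Month 6. EOS at Month 18 (F = 6) or Month 16 (F = 4) is then about 12 or 10 months after the last cenerimod dose.

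**The case against.** **The tables are descriptive, and time-based PK work sits elsewhere.** Section 6.10 plans no half-life or dose-proportionality analysis. SAP section 1 assigns PK parameters and individual and mean concentration-time profiles to the clinical pharmacologist, with concentrations merged with actual sampling times. The full protocol Version 5 is not among the documents, so a further PK plan cannot be ruled out. This stands and limits the consequence. It does not change what 6.10.2 will tabulate and plot.

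**Samples can be excluded.** Section 4.1.8 provides for this. It stands in part: without criteria, nothing tells the programmer to remove or separate these samples.

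**The 12–22 day half-life is superseded.** This stands. A longer value shrinks the ratios, which is why 30 and 40 days are shown. A several-fold spread remains.

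**Many subjects do have a defined EOS time.** Version 5 completers are at 6 months ±7 days, and Placebo / Ex-4 mg is a separate group in combined analyses up to EOS (5.4.3.3). This stands too: the undefined quantity is the pooled mean, not each subject's sample.

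**Stronger readings to resist.**

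- A reader might put a percentage on the trough bias by assuming, say, 10% of subjects are 60 days off drug. The 10% has no source. Sixty days off drug is impossible at Month 1, and at Month 2 needs a stop within about the first week.
- A reader might infer that follow-up was lengthened because of the half-life. The revision history links the half-life evidence to the treatment-emergent window only and gives no reason for the extension.
- A reader might infer that the trial will report a wrong half-life. None is planned from these tables.

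**Conclusion.** The point holds as an inexpensive improvement to descriptive PK reporting. As written, 6.10.2 gives one EOS geometric mean per group over samples about 4, 6 and up to nearly 12 months after EOT. It gives one premature EOT mean over every stage of accumulation, and Month 1 to 3 columns that can mix on-drug and off-drug samples. Between 4 and 6 months the expected concentration differs 6.6- to 32-fold at the documented half-life, and 4.0- to 2.8-fold at assumed half-lives of 30 to 40 days. Between 6 months and 350 days the assumed values give 51- to 19-fold.

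This rests on first-order decay and on some subjects falling in each timing group; the share with 4-month follow-up is not given. No efficacy test or error rate is touched.

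**What to change.** In SAP 6.10.2:

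- **Trough columns.** Limit the Month 1, 2, 3, 6 and 12 summaries to samples taken while on cenerimod, judged by actual intake dates. List the others.
- **EOS.** Replace the single column with summaries and a plot by days since last cenerimod intake, split at least into about 4 months, about 6 months and later.
- **Premature EOT.** Present by days since last cenerimod intake and by treatment duration.
- **Placebo / Ex-4 mg.** Count from the last cenerimod intake, not from overall EOT.

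Two related gaps can be closed in the same edit. Section 6.10 reads as pre-dose sampling at premature EOT and EOS while footnote 9 allows any time in the visit, so the two need to be reconciled. Section 6.10 also states no rule for values below quantification, which a geometric mean needs at these intervals.

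The cost is SAP wording and table programming. Sampling times are already merged (SAP section 1) and intake dates are in the treatment log (5.1), so no new data are needed. The downside is fewer samples per column.
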